6 STUDY INTERVENTION(S) OR EXPERIMENTAL MANIPULATION(S)

6.1 STUDY INTERVENTION(S) OR EXPERIMENTAL MANIPULATION(S) ADMINISTRATION

6.1.1 STUDY INTERVENTION OR EXPERIMENTAL MANIPULATION DESCRIPTION

MASLIHAT Intervention. MASLIHAT’s 5 sessions are based on the SHIELD model and the social cognitive theory that drives it.³⁵ Drawing on Yang’s theory of migration,²² we also added issues and risk-reduction strategies to address the challenges of migrant life that contribute to high-risk behavior. We expect MASLIHAT to produce positive change in peer educators’ and network members’ condom use, needle hygiene, and safer alcohol use. Primary outcome measures are syringe sharing in the past 3 months, and vaginal or anal sex without a condom in the past 3 months. Other measures include syringe cleaning methods, and the Alcohol Use Disorder Identification Test (AUDIT) to assess alcohol consumption and alcohol-related problems at each time point. In addition to risk behavior, we will assess theoretical mediators including HIV knowledge, risk awareness, behavioral norms, self-efficacy, depression, and loneliness.

The intervention consists of five 2-hour sessions delivered to participants recruited as peer educators who meet as a group once a week for five weeks. Light refreshments are provided. The content of the 5 sessions, which are specified in detail in the MASLIHAT facilitators’ manual, focus on: 1) An introduction

to MASLIHAT and its goals; general risks and safety for Tajik migrant workers; living a healthy life style, resources & organizations serving Tajik migrants; 2) HIV 101; peer communication skills; 3) HIV/STI risk/prevention thorough safer sex; alcohol use and HIV risk; 4) HIV risk/prevention related to injection drug use; and 5) Maintaining a healthier life style; sustaining peer outreach. Homework assignments and case studies in each session help to script peer educator messages to deliver to network peers.

Control Condition. The Healthy Lifestyle for Labor Migrants program was designed by Drs. [name] and [name] to serve as a control condition in testing an HIV prevention model delivered to Tajik migrants traveling from Dushanbe to Moscow by train.³⁶ Since few migrants in the last 5 years have traveled to Russia by rail as air travel is so much faster, neither the train intervention or the TANSIHAT program are currently being delivered. Fully manualized, the original Healthy Lifestyle program consists of three modules that provide information about general risks to health, healthy nutrition, personal hygiene, fitness, and stress management. This program provides relevant health information for Tajik migrant workers (including prevention of cardiovascular disease, the most common cause of death in Tajikistan), and encourages participants to share the information with other migrants, but it does not address HIV/STI risk and prevention, condom use, or drug use.

We have designed additional content and organized the program to consist of five sessions to parallel the MASLIHAT intervention in terms of time commitment. Additions include information on workplace safety and an added emphasis on strategies for avoiding respiratory infections (TB, COVID19) as these are important health issues in Russia among labor migrants. The content of the 5 sessions, which are specified in detail in the Healthy Lifestyle facilitators' manual, focus on: 1) understanding health risks facing Tajik migrants in Moscow; 2) healthy nutrition and personal hygiene; 3) fitness and stress management; 4) workplace safety; and 5) prevention of respiratory infections.

6.1.2 ADMINISTRATION AND/OR DOSING

The MASLIHAT and TANSIHAT interventions will be delivered in 5 weekly small group sessions led by a trained facilitator. Sessions will take place at the PRIZMA Research Center. MASLIHAT sessions include group discussions and interactive role-playing activities to practice the communication and outreach skills. MASLIHAT treatment dosage effects for peer educators will be measured by: (1) total number of sessions attended, and (2) specific sessions attended.

6.2 FIDELITY

6.2.1 INTERVENTIONIST TRAINING AND TRACKING

Facilitator qualifications and training. Four facilitators will be hired and trained by Drs. [name], [name], and [name] to co-lead the MASLIHAT sessions using the Facilitators' Guide developed in the pilot study and the control group sessions using the TANSIHAT manual. To qualify, each facilitator must be a Tajik migrant with experience in conducting group sessions. We also will screen for facilitators who are non-judgmental and well respected within the Moscow Tajik migrant community. Two facilitators will be trained to deliver the MASLIHAT sessions, and two will be trained to deliver TANSIHAT. Facilitator

training will include a refresher on basic group facilitation skills (e.g. communication skills, etc.), as well as training on the intervention background, structure, and content. Facilitator training will begin with [name] and [name] presenting the entire program to the trainees so that they can become familiar with the content and observe the role of the facilitator. Next, facilitator trainees will receive 3 days of training led by Drs. [name] and [name], and guided by the MASLIHAT or TANSIHAT Manual in how to facilitate the intervention sessions. Finally, trainees will receive practice in delivering the intervention with a small group of MWID (day 5).

- Day 1: Introduction and MASLIHAT / TANSIHAT presentation
- Day 2: Basic group facilitation skills and practice; Session 1 training and practice
- Day 3: MASLIHAT / TANSIHAT sessions 2 & 3 training and practice
- Day 4: MASLIHAT / TANSIHAT sessions 4 & 5 training and practice
- Day 5: MASLIHAT / TANSIHAT live practice

Fidelity to the MASLIHAT and Healthy Lifestyle Models. Our process evaluation is designed to check whether or not the interventions are being delivered and implemented with fidelity to the two models. Five methods will be used. 1) The MASLIHAT and Healthy Lifestyle facilitators' manuals will provide a detailed guide as to the content and procedures for each specific session. 2) Facilitators will be rigorously trained in how to use the manuals and deliver each of the 5 sessions. 3) [name] and/or the Project Coordinator ([name]) will observe and summarize in writing their perception of the facilitators' and sessions' fidelity to the particular model at the end of each session and provide further training or guidance if needed. All sessions will be audio recorded. [name] will audit the recordings, and randomly selected sessions will be translated and transcribed for independent review by the U.S. investigators. 4) Each facilitator will fill out a project-prepared assessment form recording his perception of where each session succeeded and/or deviated from what was planned and strategies devised by facilitators and project staff to enhance fidelity if appropriate. 5) As part of its members' duties, the CAB will meet annually to review the study's progress and to assess its fidelity in delivering the interventions.

6.3 MEASURES TO MINIMIZE BIAS: RANDOMIZATION AND BLINDING

The 12 recruitment sites will be pair matched and randomly assigned to a study arm. One of each pair will be assigned to MASLIHAT and the other to the control condition. [name] will create the matched pairs based on site characteristics, and randomization will be determined by the PI using a random number generator. A random number will be generated for each site, and within each matched pair, the site with the smaller number will be assigned to MASLIHAT. To minimize bias during recruitment, site assignments will be masked from project staff engaged in recruitment. The PI will inform the Moscow project coordinator of the site assignment as needed for group scheduling, after the first cohort of participants has been filled for the site. Participants will be informed of their assignment at the time of scheduling the group sessions. [name] will also have access to this information as needed, after recruitment activities are underway. Interviewers will be blinded to site assignment, and the same interview instrument will be used for MASLIHAT and control condition participants. Session facilitators, who may become aware of the recruitment sites from which participants originated, will be instructed during training not to reveal this information to interviewers. Intentional or unintentional breaking of the blind is to be reported to the PI.

The randomization codes will be kept in a password-protected file accessible to the PI, co-investigators, the project coordinator, and the data manager. When preparing data for analysis, the data manager will

blind code recruitment site and study arm. Masking will be removed for reporting interim results to the DSMB.

In addition, we will adopt a position of clinical equipoise. Intervention facilitators and interviewers will be informed that we are testing two different interventions, but neither is assumed to be superior to the other. Facilitators will be assigned to one or the other, while interviewers will be blinded to participant condition. Data collection will be conducted by interviewers who are not involved in intervention delivery. Interviews will be standardized using a computer-assisted instrument, and sensitive sections will be self-administered.

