5.5 STRATEGIES FOR RECRUITMENT AND RETENTION

The study will enroll a total of 420 male Tajik migrant MWID including 140 index participants (MASLIHAT or control intervention) and 280 IDU network members. Based on pilot study experience, since recruitment materials will specify the requirements for participation, nearly all men who present for screening will meet the criteria for enrollment. We anticipate screening up to 150 MWID for participation as index participants, and up to 300 MWID for participation as network members.

Timing for recruitment. Recruitment of index participants (70 MASLIHAT peer educators and 70 control group participants) will take place throughout the intervention/baseline data collection period (18 months) through referrals from the Tajik diaspora organizations and recruitment at the 6 worksites and 4 bazaar sites until sample requirements for 140 index participants are met. Network member recruitment (n=280) will occur through referral by the index participants. As with the pilot study, only

index participants who successfully recruit two eligible network members will participate in the interventions. Recruitment will be conducted intensively at two sites at a time, one assigned to the intervention and the other to the control. We will recruit from these sites until we have filled two groups of 5 to 7 eligible participants (each having successfully recruited 2 network members). Groups will be closed to new members after the first session. When we have filled 2 groups for each site in the pair, the recruitment team will move on to the next pair of sites. We will run four intervention groups each quarter (2 MASLIHAT and 2 TANSIHAT) over a period of 18 months (20 groups total).

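### Releasing one site's arm can reveal its paired site's arm while that site's first group is still being recruited

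*Combined protocol and SAP*

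**What the plan says.** **Allocation.** Section 6.3: "The 12 recruitment sites will be pair matched and randomly assigned to a study arm". The allocation is a block of two: "One of each pair will be assigned to MASLIHAT and the other to the control condition". A random number is drawn for each site, and "within each matched pair, the site with the smaller number will be assigned to MASLIHAT".

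**Recruitment order.** Section 5.5: "Recruitment will be conducted intensively at two sites at a time, one assigned to the intervention and the other to the control". Each site fills two groups: "We will recruit from these sites until we have filled two groups of 5 to 7 eligible participants". The next sentence on sequence shows that the two concurrent sites are the matched pair: "When we have filled 2 groups for each site in the pair, the recruitment team will move on to the next pair of sites".

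**Release.** Section 6.3: "The PI will inform the Moscow project coordinator of the site assignment as needed for group scheduling", and this may happen "after the first cohort of participants has been filled for the site". Men learn their arm when their sessions are scheduled. Section 6.3 also says that recruiting staff are masked to site assignment, and it lists the coordinator among those who can open the randomization file, with no time limit.

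**Who decides eligibility.** Section 5.5, under recruiting network members, has the coordinator screen callers, confirm index eligibility at the enrollment visit and verify network members. Section 8.1 has a trained interviewer screen both kinds of participant, and 10.1.1.2 also has the interviewer document screening. Under 6.3, interviewers are blinded.

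**The concern.** The release rule works site by site, but the allocation works pair by pair. Concealing a site's arm until its own first group is full protects that group only if nothing else discloses the arm. With one site of each pair in each arm, the partner's release does disclose it. Because the two sites recruit in parallel, the slower one may still be enrolling its first group when that happens.

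At stake is concealment at the point of entry. In a cluster trial with self-reported primary outcomes and only six pairs, differences between arms in who is enrolled cannot be relied on to average out.

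The step that makes this more than a formality is the coordinator's role in 5.5. There is room for judgment in it: when injection marks are not visible, eligibility rests on questioning (5.5 and 8.1), rescreening is optional (5.4), and a group may close at 5, 6 or 7 men.

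**Working it through.** The plan gives no figure on this point, so there is nothing to reproduce. The check has two parts.

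**1. Can the partner's arm be deduced?**

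- Six pairs give 2^6 = 64 possible allocations. In all 64 the two sites of a pair are in opposite arms, so once one arm is known the other is known with probability 64/64 = 1.
- For comparison, if 6 of 12 sites were drawn for each arm without pairing, the chance that a given other site is in the opposite arm would be 6/11 = 0.545.
- Nothing in 5.5 or 6.3 hides the pairing, staggers the two sites or ties release to the partner. One site per pair, so up to 6 of the 12, can have its arm deduced before its own first group is full.

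**2. How many first-group places could be open at that moment?**

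Inputs from the documents: two sites per pair and two groups of 5 to 7 per site (5.5). Assumptions, because the documents give no fill rates: places fill one at a time, the next place in the pair goes to one site with probability p and to the other with q = 1 − p, and release comes as soon as the first site's group fills.

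With group size n, the probability that the slower site has filled k places when the faster one reaches n is

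P(k) = C(n−1+k, k) × (pⁿqᵏ + qⁿpᵏ), for k = 0, …, n−1,

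and the mean number of open places is Σ (n − k) P(k).

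For n = 6 and equal rates (p = 1/2):

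| k filled | 0 | 1 | 2 | 3 | 4 | 5 |
|---|---|---|---|---|---|---|
| P(k) | 0.031 | 0.094 | 0.164 | 0.219 | 0.246 | 0.246 |
| open places | 6 | 5 | 4 | 3 | 2 | 1 |

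Sum of products: 0.188 + 0.469 + 0.656 + 0.656 + 0.492 + 0.246 = 2.71.

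A pair holds 2 sites × 2 groups × n index men, that is 4n. Over the permitted group sizes:

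| n | Open places, 1:1 | Share of 4n | Open places, 2:1 | Share of 4n |
|---|---|---|---|---|
| 5 | 2.46 | 12.3% | 2.95 | 14.8% |
| 6 | 2.71 | 11.3% | 3.40 | 14.2% |
| 7 | 2.93 | 10.5% | 3.86 | 13.8% |

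At these fill rates the shares are upper figures. A place is filled only when the index man has brought in two network members (5.5), on coupons valid for 30 days (8.1). Some of the men who will take the open places have therefore already been screened and have consented when the faster site fills, and the model still counts them as exposed. A more uneven pair would raise the figure, up to n/4n = 25% if the slower site had filled no place.

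**The case against.** **Release is permitted, not automatic.** Section 6.3 sets an earliest moment and ties release to scheduling needs. If the PI waits, or if both sites fill together, nothing leaks. This stands. A reader might infer that the slower site of every pair is always affected, and the documents do not support that. Nor do they require the PI to wait.

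**The route to bias is narrow.** A reader might infer that invitation itself could depend on the arm. Sections 5.5 and 6.3 do not support this: recruiters are blinded, cards and flyers go out through diaspora staff, brigade leaders and worksite managers, and index men choose the network members. Nearly all men who present are expected to qualify. Interviewers are blinded, and sensitive questions are self-administered. All of this stands. What remains is the coordinator's screening and verification in 5.5. Section 8.1 would remove most of that if it governs, so the two sections must be reconciled.

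**A later site-by-site release would do nearly as well.** If each arm were released only after that site's own two groups had filled, the same model with n = 6 leaves 0.27 open first-group places at the partner instead of 2.71 at equal rates, and 1.18 instead of 3.40 at 2:1. This partly stands: delay at each site reduces the exposure but does not end it, and what remains falls mainly on the partner's second group.

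**Larger gaps exist.** Second groups are enrolled after their own site's release, and the coordinator's file access has no time limit. Both points are right. A pair-level release rule alone would leave them open, so the fix has to cover them.

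**Conclusion.** The concern holds as a possibility that the plan leaves open. Sections 5.5 and 6.3 together allow the slower site's arm to be deduced with certainty while its first group, the one the release rule is meant to protect, is still open. It happens only if release comes before the partner has filled. It matters mainly through the coordinator's eligibility role in 5.5.

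With groups of 6, one-at-a-time filling and immediate release, the partner would have 2.7 of 6 first-group places open at equal rates and 3.4 at 2:1, at most about 11% to 14% of index men at those rates. A reader might take that as the share of the sample that is biased. It is not. It counts men who could be enrolled while the arm was deducible, and the documents give no basis for estimating any selection that results. This is a cheap improvement to the plan, not a flaw that undermines the trial.

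**What to change.** In 6.3, replace the site-level release with a pair-level one:

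1. Neither site's arm in a pair is released to the coordinator or to participants until the first groups of both sites have filled and all index and network men in those groups have completed the baseline interview.
2. The coordinator has no access to the randomization file until that point.
3. Because second groups are recruited after release, eligibility for all groups is decided by the blinded interviewers, as 8.1 already describes. Amend 5.5 to agree.

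Under the first two changes, the number of sites whose arm can be deduced before their own first group fills falls from up to 6 of 12 to 0 of 12. The third limits what a known arm can influence in the second groups. The coordinator would still take preliminary calls and make appointments under 8.1.

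**Cost.** A few sentences in 6.3 and 5.5, with the Manual of Procedures to match, and no change to the planned sample. The faster site waits for its partner; the documents do not allow the wait to be estimated. The wait carries some risk. Section 5.5 notes that migrants can drop out of contact unexpectedly, and under 5.2 an index man who misses the first session is excluded, so some extra screening and replacement may be needed.

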8 STUDY ASSESSMENTS AND PROCEDURES

8.1 ENDPOINT AND OTHER NON-SAFETY ASSESSMENTS

Eligibility pre-screening. Potential index and network participants will call the PRIZMA Research Center for preliminary screening. The project coordinator will explain the study requirements and schedule an appointment for the enrollment visit (index participant) or enrollment and baseline interview (network member).

Screening & Enrollment. Participant screening, enrollment, and informed consent will take place in a private room at the PRIZMA office. A trained interviewer will interview each potential subject for the intervention conditions or as network members to identify those who meet the criteria to participate. Injection drug use will be confirmed by the presence of injection marks (tracks), or if marks are not visible, asking the subject about the injection process using a series of questions designed to identify PWID. The interviewers will then explain the purpose and activities of the study to eligible subjects and obtain informed consent from those who indicate their willingness to participate. Contact information also will be collected from the enrollees for follow-up purposes and the participants will be given contact information for the study coordinator should they have further questions.

Index participants. Project staff will confirm the participant's willingness to recruit two other Tajik migrant MWID for interviewing. Participants will complete a brief social network survey to enumerate their IDU network, and they will be given two coupons to recruit network members who meet the study criteria for interviews. Coupons will be valid for 30 days. Index participants will return to complete the baseline interview after network participants have enrolled.

Network participants. Project staff will check the participant's recruitment coupon and confirm his relationship to the index person who recruited him before continuing to administer the baseline interview.

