Interviews: Intervention participants and network members will complete computer-assisted personal interviews (CAPI) at baseline (prior to first intervention session), and at 3, 6, 9, and 12 months post-intervention. All baseline and 12-month interviews will be conducted in a private room at the PRIZMA office; intermediate follow-up interviews may be conducted at the PRIZMA office or at a location selected by the subject. Trained interviewers will administer the 60 to 90-minute questionnaire, using a computer-assisted personal interview (CAPI) system (Qualtrics) to record responses. For the more sensitive questions such as sexual behavior and STIs, the interviewer will instruct the participant to enter his responses. The CAPI system will ensure proper administration of skip sequences. For quality control purposes, 20% of interviews will be randomly selected to be audiotaped, and half of these audiotapes will be reviewed by [name] or [name] for quality assurance. Using electronic data capture and requiring timely data uploads will allow the data manager to monitor research progress and conduct quality control checks. The questionnaires were developed and tested with members of the population using cognitive interviewing (CI).⁶² Translations were validated using "back translation" with a member of the study population.

Self-report Measures

Background measures. The baseline interview includes measures of basic sociodemographic variables (education, marital status, migration history, religion), community involvement/social activities, and health (general health, STIs). The follow-up interviews also collect self-reported STIs since last interview.

Outcome measures. Primary outcome measures are syringe sharing in the past 3 months, and vaginal or anal sex without a condom in the past 3 months. Other measures include syringe cleaning methods, and the Alcohol Use Disorder Identification Test (AUDIT)⁶³ to assess alcohol consumption and alcohol-related problems at each time point.

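### Index participants can give their self-reported baseline after learning their arm, because disclosure is tied to scheduling and the baseline interview only to the first session

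*Combined protocol and SAP*

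**What the plan says.** Four rules bear on the order of events for an index participant.

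- **Disclosure (6.3).** "Participants will be informed of their assignment at the time of scheduling the group sessions". The project coordinator is given the site's arm as needed for scheduling, "after the first cohort of participants has been filled for the site".
- **When a group is full (5.5).** Recruitment at a site continues "until we have filled two groups of 5 to 7 eligible participants (each having successfully recruited 2 network members"). A completed index baseline is not part of this condition.
- **When the index man is interviewed (8.1).** He consents and receives coupons valid for 30 days. Then: "Index participants will return to complete the baseline interview after network participants have enrolled".
- **Deadline for baseline (8.1).** Participants "complete computer-assisted personal interviews (CAPI) at baseline (prior to first intervention session"). No other limit is given in the interview text.

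Network members are handled differently: 8.1 books them for "enrollment and baseline interview (network member"), so their baseline takes place when they enrol.

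The schedule of activities (1.3) puts consent and the baseline interview together on Visit 1, Day 1, and the first session on Day 7±3. It does not mention scheduling of groups or disclosure of the arm.

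**The concern.** Disclosure and baseline hang on different events, and no sentence orders the two. The programmes are easy to tell apart: one trains men as HIV-prevention peer educators, while the other leaves out HIV, condoms and drug use (4.2, 6.1.1). A man who knows which he will attend may describe his past three months differently from one who does not.

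Syringe sharing and condomless sex, the primary outcome measures named in 8.1, are self-reported. Section 9.4.2 tests the effect of condition on change in them, so a baseline shift that differs between arms feeds into the quantity being tested. Participants cannot be masked at follow-up in this design. Baseline is the one self-report measurement that can be.

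**Working it through.** No stated figure needs reproducing. The check is whether any text forces baseline to come first.

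**Step 1: the sequence for one index man.**

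1. He consents and receives coupons (8.1).
2. His two network members enrol and are interviewed (4.1, 8.1). He now counts toward a filled group (5.5).
3. The group is filled and its sessions are scheduled. He is told his arm (6.3).
4. He returns for his baseline interview, at any time after step 2 and before step 5 (8.1).
5. First session.

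Steps 3 and 4 both follow step 2 and precede step 5. Nothing fixes their order relative to each other.

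**Step 2: who is most exposed.**

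- *The last man to complete a group.* The event that fills the group, enrolment of his recruits, is also the event that lets him return for baseline. Scheduling can start before he does.
- *Possibly men in a site's second group.* For the first group, the coordinator does not know the arm until it is filled. For the second, the coordinator already knows it, and also screens callers and books visits (5.5, 8.1). That safeguard is gone, although the disclosure trigger is still scheduling.

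**Step 3: does the schedule of activities close the gap?**

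- If Day 1 is the consent visit, session 1 falls between Day 4 (7 − 3) and Day 10 (7 + 3). That does not fit 30-day coupons followed by a return visit.
- If Day 1 is the baseline visit, session 1 falls 3 to 9 days later (4 − 1 to 10 − 1). Five to seven men share one start date, so sessions would probably already be booked when those baselines take place.

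On neither reading does 1.3 guarantee that baseline precedes disclosure.

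**Step 4: scope.** Index participants are 140 of 420, and 140 / 420 = 0.33. The 280 network members have baseline at enrolment, before their index man counts toward a filled group. They are largely protected, though a first group at the same site may already know the arm when later network members enrol.

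**Step 5: how a shift would act.** On a simple additive scale, let b be the average shift in an arm's baseline reports caused by knowing the arm, and f the corresponding shift at follow-up. The bias in the between-arm difference in change is

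(f_MASLIHAT − f_control) − (b_MASLIHAT − b_control).

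Each b is the share of men interviewed after disclosure times the average shift among them. The documents give neither the share nor any shift, so the expression cannot be evaluated, even for its sign.

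**The case against.** The best counter-argument is that nothing says baseline will follow disclosure. Many first-group men would probably be interviewed before their group fills, 1.3 treats baseline as an enrolment-stage procedure, interviewers are blinded, and 6.3 and 8.1 have sensitive items entered by the participant. All of this stands as mitigation. It does not close the gap: blinding and self-entry reduce pressure from the interviewer but do not remove the respondent's knowledge of his own arm, and 1.3 conflicts with 8.1.

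A reader might infer more than the documents support:

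- *That men disclose sharing and condomless sex to a face-to-face interviewer.* Section 8.1 has sexual behaviour self-entered. Syringe sharing is not named there, so its mode is not established either way.
- *That half the index men, namely all second groups, are affected.* The coordinator knowing the arm does not mean the men know it; they are told at scheduling, like everyone else.
- *That the bias equals the baseline shift.* This holds only if follow-up reports carry no arm-related shift. All index men know their arm at follow-up, so a shift present at both times partly or wholly cancels. Under-reporting at baseline in MASLIHAT alone would work against finding an effect.
- *That baseline comparability can no longer be checked on masked data.* Section 6.3 has the data manager blind-code site and arm, and telling participants does not undo that.

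**Conclusion.** The point holds for index participants as a gap in sequencing: the protocol permits, but does not say, that baseline follows disclosure. It directly concerns at most 140 of 420 participants. The primary model analyses both participant types together unless the interaction reaches p < .10 (9.4.2), so any effect on a pooled estimate would be diluted by the network members.

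The number of men interviewed after disclosure, and the direction and size of any bias, are unknown. No bias figure should be attached. The conclusion rests on reading 5.5, 6.3 and 8.1 as written and assumes no unpublished procedure that already fixes the order. It is worth correcting because masking baseline costs little and later measurements cannot be masked.

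**What to change.** In 6.3 and 8.1, state for both groups at every site that an index participant is not told his arm until his baseline interview is completed and uploaded. Until then, his sessions are booked by date and place only, with no programme named. His network members' baselines already come first, so they need no added rule.

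Record the date of disclosure and the date of baseline for each index man, so that the order can be verified and any exceptions reported. Reconcile the Day 1 and Day 7±3 entries in 1.3 with the return visit and 30-day coupons in 8.1.

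The cost is a small scheduling check by the coordinator, with no extra visits, staff or participants.
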